#### **Methods and Procedures**

The trial is designed to prove the efficacy and safety of the invisa-RED Technology Elite Low-level Laser Therapy (LLLT) device. The trial will compare results between two groups; the first will be treated using a fully functional invisa-RED Technology Elite device; this group will be internally designated the Usual Care Group. The second, a control group, will be treated utilizing a nonfunctional invisa-RED Technology Elite device; this group will be referred to internally as the Sham Group.

The sham device will consist of an invisa-RED Technology Elite device that will appear to operate as the Usual Care Group device to the operator, but the laser diodes will be disabled and will receive no power. If staff or a participant questions the efficacy of the sham device, an assertion may be made that only a near infrared, nonvisible frequency of light, is being employed.

The trial will be conducted employing a double blind study methodology; participants will be randomly assigned to each group through a drawing, neither participants nor clinicians will know to which trial group they are assigned. To ensure the double blind; treatment for the two groups will occur on separate days of the week. All participants will receive therapy at the [name] Chiropractic Center located in Hixson, TN. Group 1 will be assigned Monday, Wednesday, Friday, and Group 2; Tuesday, Thursday, and Saturday. Additionally staff administering the trial therapy will be assigned to work with one (1) group exclusively.

A simplified weight loss protocol will be employed based on the "Consultation Protocol" from the invisa-Red Training Manual. All study participants will undergo nine (9) therapy sessions of 20 minutes each; using a singular protocol setting for pulse (3.5s) and delay (0.2s), but power settings will be based on the participants Fitzpatrick Scale skin type. For skin types i and ii a power setting of 7 will be used, for skin types iii and iv a power setting of 6, for skin types v and vi a power setting of 4 will be employed. At the conclusion of the nine (9) therapy sessions; the change in body fat percentage, weight, and inches lost of the two groups will be statistically analyzed to determine the efficacy of the invisa-RED Technology Elite as a weight loss therapy. Any medical errors will be included in the statistical analysis.

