### **Data Analysis and Data Monitoring**

The measured weight loss and total inches lost per participant from the two groups will be statistically evaluated using an Independent T-Test with a P value of .05.

The study is classified as a minimal risk trial of short duration therefore a detailed plan for monitoring the data for participant safety is not required.

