Statistical Analysis Plan

Cover Page

for the Clinical Study

"Comparing the Efficacy of a Dual-Frequency Laser-Emitting Device, the "invisared-RED Elite", With a Sham Device as Therapy for the Loss of Adipose Tissue (Body Fat) and Aesthetics in Overweight Individuals"

NCT03811093

May 7, 2019

Statistical Analysis Plan

for

Invisa-RED Clinical Trial

Research Questions:

Research Question One (1): Is there a statistically significant difference in Percentage of Body Fat Lost when using an invisa-RED Technology Elite Low-level Laser Therapy (LLLT) device when compared with a sham (placebo) device in an approved and standardized clinical protocol?

Null Hypothesis One (1): There is not a statistically significant difference in Percentage of Body Fat Lost when using an invisa-RED Technology Elite Low-level Laser Therapy (LLLT) device when compared with a sham (placebo) device as a therapy in an approved and standardized clinical protocol.

Alternative Hypothesis One (1): There is a statistically significant difference in Percentage of Body Fat Lost when using an invisa-RED Technology Elite Low-level Laser Therapy (LLLT) device when compared with a sham (placebo) device as a therapy in an approved and standardized clinical protocol.

Research Question Two (2): Is there a statistically significant difference in Inches Lost when using an invisa-RED Technology Elite Low-level Laser Therapy (LLLT) device when compared with a sham (placebo) device in an approved and standardized clinical protocol?

Null Hypothesis Two (2): There is not a statistically significant difference in Inches Lost when using an invisa-RED Technology Elite Low-level Laser Therapy (LLLT) device when compared with a sham (placebo) device in an approved and standardized clinical protocol.

Alternative Hypothesis Two (2): There is a statistically significant difference in Inches Lost when using an invisa-RED Technology Elite Low-level Laser Therapy (LLLT) device when compared with a sham (placebo) device in an approved and standardized clinical protocol.

Research Question Three(3): Is there a statistically significant difference in Pounds of Body Fat Lost when using an invisa-RED Technology Elite Low-level Laser Therapy (LLLT) device as a therapy when compared with a sham (placebo) device in an approved and standardized clinical protocol?

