Null Hypothesis Three (3): There is not a statistically significant difference in Pounds of Body Fat Lost when using an invisa-RED Technology Elite Low-level Laser Therapy (LLLT) device when compared with a sham (placebo) device as a therapy in an approved and standardized clinical protocol.

Alternative Hypothesis Three (3): There is a statistically significant difference in Pounds of Body Fat Lost when using an invisa-RED Technology Elite Low-level Laser Therapy (LLLT) device when compared with a sham (placebo) device as a therapy in an approved and standardized clinical protocol.

Data Sets/Populations:

Criteria for Participants:

Participants will be taken from a random population of respondents to both email and social media recruitment. The number of participants is projected to be forty (40). There will be an equitable distribution of male and female participants. Women who are pregnant, trying to get pregnant, or nursing will be excluded from the study, as they should not receive Low-level Laser Therapy (LLLT). Note; there is no evidence of harm to an unborn baby however there have been no safety tests either, so for medical legal reasons we recommend never treating such individuals. The participants will be between the ages of 18-75 years. Inclusion criteria will be individuals that may benefit from a weight loss therapy.

Exclusion criteria will include the following:

- If you are pregnant, trying to get pregnant or nursing laser light therapy should be received only after the end of these conditions. There is no evidence of harm to an unborn baby however there have been no safety tests either, so for medical legal reasons we recommend never treating areas directly over a developing child.
- Individuals with hypertension, light sensitive epilepsy, cancer, heart disease, infectious skin disease, and severe varicose veins should not use this device.
- People suffering from infectious and acute disease such as a fever should not use this device.
- People who have hemorrhagic disease, vascular ruptures, skin inflammation, or any disease of the skin should not use this device.
- People who have immune system dysfunction such as Leukemia, Hemophilia, etc., and light sensitive persons should not use this device.
- Individuals with a history of melanoma, raised moles, suspicious lesions, keloid scar formation, or healing problems should not undergo laser light therapy.

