- Individuals with active infections, open lesions, hives, herpetic lesions, cold sores, or tattoos and permanent make-up in the area of treatment should not undergo laser light therapy.
- People who have used isotretinoin (commonly known as Accutane), tetracycline, St. John's Wort, or any photo sensitizing drugs in the last year should not undergo laser light therapy.
- Individuals with autoimmune diseases such as Lupus, Scleroderma, or Vitiligo should not undergo laser light therapy.
- Individuals who have pacemakers or other electro-stimulation devices surgically implanted should not undergo laser light therapy.
- Any insulin dependent individual should consult their physician before undergoing laser light therapy.
- All individuals considered "vulnerable" such as children, pregnant women, nursing home residents or other institutionalized persons, students, employees, fetuses, prisoners, and persons with decisional incapacity.

From the population of prospective participants screened using the above criteria, each of the approximately 40 participants selected will be randomly assigned to one of two groups; the Care as Usual Group or the Sham (placebo) Group.

Analysis:

To examine the three (3) research questions, independent sample *t*-tests using the statistical analysis program SPSS will be conducted on the three comparative data sets. Each of the three data sets will be comprised of comparative results from the two trial groups, the Care as Usual Study Group and the Sham (placebo effect) Study Group.

Data set One (1) will be the comparative Percentage of Body Fat Lost results, Data Set Two (2) will be the comparative Inches Lost results, and Data Set Three (3) will be the comparative Weight of Body Fat Lost results.

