An independent samples *t*-test is the appropriate statistical test when the purpose of research is to assess if differences exist on a continuous (interval/ratio) dependent variable by a dichotomous (2 groups) independent variable. The three continuous dependent variables to be tested are Percentage of Body Fat Lost or Gained, Weight of Body Fat Lost or Gained, and Total Inches Lost or Gained. The dichotomous independent variables for the three data sets are the invisa-RED Technology Elite Low-level Laser Therapy (LLLT) device and the sham (placebo) device, each administered as therapy in a standardized clinical protocol. The assumptions of normality and homogeneity of variance will be assessed. Normality assumes that the scores are normally distributed (bell-shaped) and will be assessed using the One-Sample Kolmogorov-Smirnov test. Homogeneity of variance assumes that both groups have equal error variances and will be assessed using Levene's Test for the Equality of Error Variances.

Each t-test will be two- tailed with the probability of rejecting the null hypothesis when it is true set at $p < 0.05$. This ensures a 95% certainty that the differences did not occur by chance. *The first t-test* using Data Set One (1) will assess if statistically significant differences exist on the dependent variable Percentage of Body Fat Lost. The second *t-test* conducted on Data Set Two (2) will assess if statistically significant differences exist on the dependent variable Inches Lost. The third *t-test* conducted on Data Set Three (3) will assess if statistically significant differences exist on the dependent variable Weight of Body Fat Lost. For each of the three data sets the independent variables are defined as an Invisia-RED Technology Elite Low-level Laser Therapy (LLLT) device and as a comparator the sham (placebo) device. Data produced by both groups will be a result of a clinical trial governed and conducted by a randomized double-blind study using an approved clinical protocol.

Reference:

Statistics Solutions. (2013). Data analysis plan: Independent Sample t-Test [WWW Document]. Retrieved from <http://www.statisticssolutions.com/academic-solutions/member-resources/member-profile/data-analysis-plan-templates/data-analysis-plan-independent-sample-t-test/>

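### All three outcomes are tested with device group as the only predictor, although baseline and sex must be on record; a prespecified adjusted analysis would remove chance imbalance in both and may improve precision

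*SAP*

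**What the plan says.** The Analysis section of the SAP plans an independent-samples t-test for each of three outcomes, two-sided at 0.05. The outcomes are changes: "Percentage of Body Fat Lost or Gained, Weight of Body Fat Lost or Gained, and Total Inches Lost or Gained". On the data, it says "Each of the three data sets will be comprised of comparative results from the two trial groups". On the predictor, it says "The dichotomous independent variables for the three data sets are the invisa-RED Technology Elite Low-level Laser Therapy (LLLT) device and the sham (placebo) device".

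The protocol (Data Analysis and Data Monitoring) says that weight loss and inches lost "will be statistically evaluated using an Independent T-Test with a P value of .05". Neither document names a covariate, an ANCOVA or a stratified analysis. The protocol (Methods and Procedures) assigns groups by a drawing and states no stratification.

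On who enters, the SAP (Data Sets/Populations) says "There will be an equitable distribution of male and female participants" and "Inclusion criteria will be individuals that may benefit from a weight loss therapy". Its cover page describes the treatment as "Therapy for the Loss of Adipose Tissue (Body Fat) and Aesthetics in Overweight Individuals", but no weight, BMI or body-fat range is set for entry. Both documents project 40 participants.

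**The concern.** Neither document lists baseline values or sex as data items, but both must exist. A loss or gain cannot be calculated without a starting value, and a balance of the sexes cannot be arranged or shown without recording sex. The plan therefore leaves unused two covariates that it already has.

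Two things are at stake. First, subtracting baseline removes only part of a chance baseline imbalance. If change is correlated with baseline, the rest stays in the one estimate the trial produces, and the same applies to an imbalance of sex if men and women change by different amounts. With about 40 people, an unstratified drawing and no entry limit on body size, sizeable imbalances are plausible. Second, if baseline and sex explain enough of the variation in change, the unadjusted interval is wider than it needs to be.

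**Working it through.** **Inputs.** From the documents: N = 40, two-sided 0.05 for each test, change scores, allocation by a drawing. Assumed, because the documents do not give them: 20 per arm, the within-arm correlation r between baseline and change (shown as its absolute size), and any sex difference in change. The plan contains no SD, power statement or sample-size calculation, so there is no figure of its own to reproduce.

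**1. Precision.** Let R² be the share of within-arm variance in change explained by baseline and sex together. Then

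adjusted variance / t-test variance = (1 - R²) × (1 + 2/(N - 5)).

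- N = 40: the penalty is 1 + 2/35 = 1.0571, so break-even is R² = 1 - 1/1.0571 = 5.4% (r = 0.23 if sex is uninformative).
- N = 30: the penalty is 1 + 2/25 = 1.080, so break-even is R² = 7.4% (r = 0.27).

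The ratio of 95% interval widths is the square root of the variance ratio times t(36)/t(38) = 1.0018. The SE of the unadjusted difference is √(2/20) = 0.316 SD of change. A 0.5 SD baseline gap shifts the unadjusted estimate by 0.5r SD of change. For N = 40, sex uninformative:

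| r | Variance ratio | Interval width ratio | Shift from a 0.5 SD baseline gap (SD of change) | Shift ÷ 0.316 |
|---|---|---|---|---|
| 0 | 1.057 | 1.030 | 0 | 0 |
| 0.1 | 1.047 | 1.025 | 0.05 | 0.16 |
| 0.2 | 1.015 | 1.009 | 0.10 | 0.32 |
| 0.3 | 0.962 | 0.983 | 0.15 | 0.47 |
| 0.4 | 0.888 | 0.944 | 0.20 | 0.63 |
| 0.5 | 0.793 | 0.892 | 0.25 | 0.79 |

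If instead r = 0 and the sexes differ by 0.5 SD in change, with half the sample of each sex, the ratio is 1.0571/(1 + 0.25/4) = 0.995, which is about break-even.

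A simulation of 20,000 trials per setting gave variance ratios of 1.053, 1.049, 1.018, 0.963, 0.888 and 0.798 for the six rows, in line with the formula.

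**2. How often imbalance arises.**

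- Baseline: the between-arm gap has SE √(2/20) = 0.316 SD, so P(gap above 0.5 SD in either direction) = 2 × (1 - Φ(0.5/0.316)) = 0.114.
- Sex: with 20 men and 20 women and an unrestricted drawing into two groups of 20, the hypergeometric probability of a 12/8 split or worse is 0.343. A 12/8 split shifts the estimate by (12/20 - 8/20) × 0.5 = 0.10 SD if the sexes differ by 0.5 SD in change, and by nothing if they do not.

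**3. Validity.** In the simulation, type I error per test was 0.049 to 0.052 for the t-test and 0.048 to 0.052 for the adjusted model. Neither analysis is invalid.

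**The case against.** The strongest reply is that the plan contains no error. A t-test on change scores is a legitimate prespecified analysis. Over repeated randomisations it is unbiased and holds its level, and its standard error already allows for chance imbalance. All of this stands.

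The gain is also unproven. Nine sessions at three a week take about three weeks, so baseline and final values may be highly correlated. If the SD is the same at both times and that correlation is ρ, then the size of r is √((1 - ρ)/2). At ρ = 0.9, 0.95 and 0.98 the variance ratios are 1.004, 1.031 and 1.047 with sex uninformative, so adjustment would be neutral or slightly costly. The 21% reduction needs ρ = 0.5. This stands as a possibility: ρ is not in the documents, and a sex effect can reverse the sign. A separate simulation in which sex explained 10% of the variance in change gave ratios of 0.86, 0.91 and 0.94 at ρ = 0.8, 0.9 and 0.98.

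The planned balance of men and women may refer to the whole sample or to each arm. The 34% figure takes the first reading, and even then the 0.10 SD shift is only about a third of the standard error. That also stands.

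Finally, the baseline is not fully defined for every outcome. The SAP does not name the sites that make up total inches, and the body-fat outcome could be read as percentage points or as a relative loss. This is a reason to write the definitions down, not a reason to leave the covariates out.

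These points limit the size of the concern. They do not remove it, because the downside of adjustment is small and the covariates cost nothing to use.

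**Conclusion.** The concern holds as a worthwhile improvement, not as a flaw that invalidates the tests. The plan uses device group alone and provides neither stratification nor adjustment, so any imbalance in a predictive baseline or in sex is only partly removed (baseline) or not removed at all (sex).

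The direction of the precision effect is unknown. With 40 analysed, the worst expected cost of adjusting is about 6% more variance and a 3% wider interval. At r = 0.5 the gain is 21% less variance and an interval about 11% narrower. With 30 analysed, the worst cost is 8% more variance. These figures rest on equal arms and on assumed correlations and sex effects. Even where precision is unchanged, adjustment removes the linear part of the imbalance that actually occurred.

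This point does not bear on a separate threat to validity. The protocol (Methods and Procedures) says "treatment for the two groups will occur on separate days of the week" and gives each group its own staff. Covariate adjustment cannot separate the device from the day or the staff.

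**What to change.** Before treatment groups are revealed to anyone involved in the analysis, amend the SAP to:

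- specify for each of the three outcomes an ANCOVA of change on device group, that outcome's baseline value and sex;
- define each baseline, including the pre-treatment total at the same measurement sites for inches, and whether body-fat loss is in percentage points or relative to the starting value;
- report the adjusted difference with a 95% confidence interval, and keep the unadjusted t-test as a sensitivity analysis;
- extend the planned assumption checks to the adjusted model (linearity and equal slopes);
- state that the adjustment does not address the link of device with treatment days and staff.

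If groups have already been revealed, the t-test should remain the planned analysis and the ANCOVA should be labelled post hoc.

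The cost is one SAP paragraph and a standard SPSS procedure, with no new data and no design change. The statistical price is two degrees of freedom and, if neither covariate predicts change, the small loss of precision given above.

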## Purpose of the Study

The trial is designed to provide the empirical data to compare the efficacy and safety of the invisa-RED Technology Elite Low-level Laser Therapy (LLLT) device with a sham device when used in the treatment of individuals for weight loss and aesthetics. At the conclusion of the trial; the change in body fat percentage, and the weight and inches lost of the two groups will be statistically analyzed to determine the efficacy of the invisa-RED Technology Elite in weight loss and/or aesthetics therapy.

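### The SAP's 95% certainty statement is wrong even for one test, and with three unranked tests at 0.05 and no success rule the error rate of the protocol's efficacy conclusion is undefined

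*SAP*

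**What the plan says.** **SAP, research questions and Analysis.** There are three numbered research questions, each with its own null and alternative hypothesis: percentage of body fat, inches, and pounds of body fat. Independent-samples t-tests "will be conducted on the three comparative data sets". The outcomes are introduced thus: "The three continuous dependent variables to be tested are Percentage of Body Fat Lost or Gained, Weight of Body Fat Lost or Gained", followed by total inches. On the level: "Each t-test will be two- tailed with the probability of rejecting the null hypothesis when it is true set at" 0.05. The next sentence reads: "This ensures a 95% certainty that the differences did not occur by chance". The tests are called first, second and third, but no test depends on the result of another.

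**Protocol, Purpose of the Study.** "the change in body fat percentage, and the weight and inches lost of the two groups will be statistically analyzed", and this is done "to determine the efficacy of the invisa-RED Technology Elite in weight loss and/or aesthetics therapy".

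**Protocol, Methods and Procedures.** "the change in body fat percentage, weight, and inches lost of the two groups will be statistically analyzed", here "to determine the efficacy of the invisa-RED Technology Elite as a weight loss therapy".

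**Protocol, Data Analysis and Data Monitoring.** A t-test at .05 is planned for weight loss and total inches only.

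Neither document names a primary outcome, a testing order, a multiplicity adjustment or a rule for what counts as success.

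**The concern.** There are three linked problems.

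1. The certainty sentence turns a conditional probability round. The sentence before it defines the level correctly, as the chance of rejecting a true null. The certainty sentence then treats its complement as the chance that an observed difference is real. A reader of the results could take any p-value below 0.05 as 95% proof.
2. The protocol uses several measures to reach an efficacy conclusion, and nothing says which result, or how many, would support it. From these two documents, the supporting outcome could be chosen after the results are known, and no error rate can be attached to the conclusion.
3. The set of outcomes is not settled. Body fat percentage is the SAP's first question but is missing from the protocol's analysis section. Weight in the protocol becomes weight of body fat in the SAP, which is a different variable.

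**Working it through.** **Inputs.** From the SAP: three tests, two-sided, 0.05 each, about 40 participants. Assumed: 20 per arm (no allocation ratio is stated), normal outcomes, and the correlations, priors and powers below (none is given).

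**Step 1. Where the 95% comes from.** For one test, 1 − 0.05 = 0.95. This is P(no rejection | no true difference).

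**Step 2. What the sentence describes.** P(real difference | significant) = q × power / [q × power + (1 − q) × 0.05], where q is the prior chance of a true difference.

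| q | power | calculation | result |
|---|---|---|---|
| 0.3 | 0.5 | 0.150 / (0.150 + 0.035) | 81% |
| 0.5 | 0.5 | 0.250 / (0.250 + 0.025) | 91% |
| 0.5 | 0.8 | 0.400 / (0.400 + 0.025) | 94% |
| 0.75 | 0.8 | 0.600 / (0.600 + 0.0125) | 98% |

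The answer may lie below or above 95%. The level alone does not ensure it.

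**Step 3. Three tests, if any one significant result were enough.** This rule is assumed; it is in neither document. With all three nulls true and independent tests, P(at least one rejection) = 1 − 0.95³ = 14.3%, and P(at least one favouring the device) = 1 − 0.975³ = 7.3%. Independence is unrealistic, since pounds of body fat is body fat percentage times body weight, so these serve only as upper limits. Simulation with 20 per arm, pooled t-tests, a common correlation and 200,000 trials per row gives:

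| correlation | any false positive | one favouring the device |
|---|---|---|
| 0.5 | 12.5% | 6.2% |
| 0.7 | 11.0% | 5.5% |
| 0.9 | 8.6% | 4.3% |
| 0.95 | 7.4% | 3.7% |

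Repeat runs at 0.5 to 0.9 differed by no more than about 0.2 points. With the two body-fat outcomes correlated 0.9 and inches correlated 0.3, 0.5 or 0.7 with both, the rates are 11.5% / 5.8%, 10.9% / 5.4% and 10.1% / 5.1%. A single two-sided test at 0.05 gives 5% / 2.5%.

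**Step 4. Does a fixed sequence repair it?** Each outcome is tested only if the one before it was significant, so any false positive requires rejection of the first true null in the order. That happens with probability at most 5%. Simulated family-wise error with all nulls true is 5.0%, 5.0% and 4.9% at correlations 0.5, 0.7 and 0.9.

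**Step 5. The outcome lists side by side.**

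| place | outcomes |
|---|---|
| Protocol, Purpose of the Study; Methods and Procedures | body fat percentage, weight, inches |
| Protocol, Data Analysis and Data Monitoring | weight, inches |
| SAP | body fat percentage, inches, weight of body fat |

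**The case against.** The strongest defence is that the SAP poses three separate questions, states its level per test and makes no family-wise claim. Three separate questions may each be tested at 0.05, and if the results are reported only as separate conclusions, that is defensible. This stands as far as the SAP goes. It does not answer Methods and Procedures in the protocol, where several measures serve one stated aim: "to determine the efficacy of the invisa-RED Technology Elite as a weight loss therapy". The wording in Purpose of the Study could mean two conclusions, one on weight loss and one on aesthetics, but no outcome is assigned to either.

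A reader might infer that the trial as planned has a false-positive rate of 14%, or of 7–13%. The documents do not support that. The first figure needs independent outcomes, and both need a rule that one significant test suffices; the documents neither state nor exclude such a rule. In the direction that would favour the device, the excess over 2.5% is only about 1 to 4 points.

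It is also fair to say that deleting the certainty sentence would change no test or threshold, and that under favourable assumptions the true figure exceeds 95%. The sentence remains false, because it says the level ensures that certainty.

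Finally, the SAP carries a registration number, and a primary outcome may be named in a record not seen here. The finding is therefore limited to these two documents.

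**Conclusion.** The point holds and should be fixed. Two parts need no assumption: the certainty sentence is incorrect for a single test, and the two documents give no primary outcome, order, adjustment or success rule and disagree on the outcomes. It follows that the error rate of the protocol's efficacy conclusion is undefined.

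The size is conditional. If one significant test were taken as enough, with 20 per arm and correlations of 0.5 to 0.95, an ineffective device would give at least one false positive in about 7–13% of trials, and one favouring the device in about 4–6%. These figures show what the missing rule could cost; they are not properties of the plan as written.

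A reader might also add to this point the protocol's assignment of separate weekdays and exclusive staff to each group. That is a separate design limitation. It does not arise from multiple testing and does not count towards the weight of this point.

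**What to change.** Make these changes before outcome data are seen by arm. If they have already been seen, say so and label the order post hoc.

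1. Name one primary outcome, for example Research Question 1 (percentage of body fat), tested at two-sided 0.05.
2. Test the others in a prespecified fixed sequence, for example the SAP's own numbering (inches, then pounds of body fat), each only if the preceding test is significant.
3. Reconcile the three protocol sections (Purpose of the Study, Methods and Procedures, Data Analysis and Data Monitoring) with the SAP. State whether weight means body weight or weight of body fat.
4. Delete the certainty sentence and put in its place: *If the assumptions of the t-tests hold, including independence of participants, the probability of one or more false-positive conclusions across the prespecified tests is at most 5%.*

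**Cost.** The sponsor must choose a primary outcome, rewrite a paragraph of the SAP and align three protocol sections. No participants are added, and the primary test keeps its full level and power. The downside is that a later outcome cannot be claimed if an earlier test fails. The change deals with multiplicity only. It does not remove shared weekday or staff effects, which is why the replacement sentence is conditional on independence.
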